### 4.1. FINAL ANALYSES

All final, planned analyses identified in this SAP are to be performed by Quintiles Biostatistics.

The following events are prerequisites for the production of any of the four interim analyses planned.

- Sponsor authorisation of the SAP and Table, Listing, Figure (TLF) shells
- Quintiles authorisation of final locked database snapshot

---

Document: CP007A SAP.docx  
Author: [name]

Version Number: V 2.0  
Version Date: 23 Feb 2017

Template No: CS\_TP\_BS016 – Revision 3  
Effective Date: 01May2012

Reference: CS\_WI\_BS005

For each interim analysis Quintiles Biostatistics will extract all data as entered in the relevant year's diary binder of each subject (there is a separate diary binder for each analysis year).

After cleaning (no outstanding data queries) of the relevant analysis year's data by DataMatica and authorisation by Quintiles Biostatistics as well as coding of all AEs and concomitant medications by Quintiles Coding, the final locked database snapshot for the relevant interim analysis (year 1, year 2, year 3 or year 4) is to be provided by DataMatica to Quintiles for the purpose of producing the interim analysis.

AEs entered in the Adverse Event Case Report Form (CRF) are to be cumulative and will not be assigned to a specific year for analysis.

- Sponsor authorisation of analysis sets

Prior to each interim analysis Quintiles Biostatistics will programmatically prepare listings of all subjects and their status with regards to inclusion or exclusion from each analysis population based on the definitions of each analysis population as described in [Section 5: Analysis Sets](#).

The listings are to be provided to Circassia for authorisation prior to each interim analysis.

---

Document: CP007A SAP.docx

Author: [name]

Version Number:

V 2.0

Version Date:

23 Feb 2017

Template No: CS\_TP\_BS016 – Revision 3

Reference: CS\_WI\_BS005

Effective Date: 01May2012

Copyright © 2012 Quintiles Transnational Corp. All rights reserved.

The contents of this document are confidential and proprietary to Quintiles Transnational Corp. Unauthorized use, disclosure or reproduction is strictly prohibited.

## 5. ANALYSIS SETS

Agreement and authorisation of subjects included/excluded from each analysis set is to be conducted annually prior to each year's interim analysis.

### 5.1. ENROLLED POPULATION [ENR]

The Enrolled population (ENR) will consist of all subjects who are consented into the study and subjects are to be listed and summarised by the treatment they were randomised to in study CP007.

### 5.2. FULL ANALYSIS SET [FAS]

The Full Analysis Set (FAS) will consist of all subjects who are consented into the study and have at least one day of symptom scores and rescue medication use recorded during the annual Allergy Evaluation Period of CP007A. Subjects are to be listed and summarised by the treatment they were randomised to in study CP007. The FAS population is to be re-assessed for each analysis year to account for subject drop-outs during each year.

### 5.3. MODIFIED INTENT TO TREAT POPULATION [MITT]

The modified Intent-to-Treat (mITT) population will consist of all subjects in the FAS who continue to live in a house with an indoor cat during the annual Allergy Evaluation Period. The mITT population is to be defined on an annual basis based on the subject's completion of the ePRO question as to whether the subject still lives in a house with an indoor cat. The mITT population may therefore change during the course of the study. Subjects are to be listed and summarised by the treatment they were randomised to in study CP007.

### 5.4. SAFETY POPULATION [SAF]

All subjects are to be included in the safety population. Safety data is to be listed and summarised by study medication actually received in study CP007.

---

Document: CP007A SAP.docx  
Author: [name]

Version Number: V 2.0  
Version Date: 23 Feb 2017

Template No: CS\_TP\_BS016 – Revision 3  
Effective Date: 01May2012

Reference: CS\_WI\_BS005

Copyright © 2012 Quintiles Transnational Corp. All rights reserved.

The contents of this document are confidential and proprietary to Quintiles Transnational Corp. Unauthorized use, disclosure or reproduction is strictly prohibited.

## 6. GENERAL CONSIDERATIONS

### 6.1. REFERENCE START DATE AND STUDY DAY

Study Day is to be calculated from the reference start date, and is used to show the start/stop day of assessments and events.

Reference start date is defined as the day of written informed consent for CP007A, (Day 1 is the day of informed consent), and will appear in every listing where an assessment date or event date appears.

- If the date of the event is on or after the reference date then:

$$\text{Study Day} = (\text{date of event} - \text{reference date}) + 1.$$

- If the date of the event is prior to the reference date then:

$$\text{Study Day} = (\text{date of event} - \text{reference date}).$$

In the situation where the event date is partial or missing, the date will appear partial or missing in the listings, and Study Day, and any corresponding durations will appear missing in the listings.

### 6.2. BASELINE

Subject data is to be obtained from the CP007 database and is used as Baseline data for CP007A.

Baseline for all efficacy variables listed in [Section 13.1](#): Primary Efficacy, [Section 13.2](#): Secondary Efficacy and [Section 13.3](#): Exploratory Efficacy is defined as the 3 week Baseline Allergy Evaluation period (Visit 2A to Visit 2B) before randomisation into study CP007.

For other Baseline characteristics Baseline is defined as follows:

- Age as entered on the Enrolment Visit CRF for CP007A
- Gender as collected at the CP007 Screening visit
- Ethnic group as collected at the CP007 Screening visit
- Asthma status as collected at the CP007 Screening visit

---

Document: CP007A SAP.docx

Author: [name]

Version Number:

V 2.0

Version Date:

23 Feb 2017

Template No: CS\_TP\_BS016 – Revision 3

Reference: CS\_WI\_BS005

Effective Date: 01May2012

Copyright © 2012 Quintiles Transnational Corp. All rights reserved.

The contents of this document are confidential and proprietary to Quintiles Transnational Corp. Unauthorized use, disclosure or reproduction is strictly prohibited.

### 6.3. STATISTICAL TESTS

All tests are two-sided, unless otherwise specified in the description of the analyses. The significance level for each analysis is specified in the relevant analysis section of the SAP.

### 6.4. COMMON CALCULATIONS

For quantitative measurements, change from Baseline is calculated as:

- Test Value at Year xx – Baseline Value

Percentage change from Baseline is calculated as:

- $[(\text{Test Value at Year xx} - \text{Baseline Value}) / \text{Baseline Value}] \times 100$

Denominator for percentages is either the total number of subjects in the analysis population or the number of subjects in the analysis population with data available for the applicable assessment and is specified in each analysis section.

### 6.5. SOFTWARE VERSION

All analyses are conducted using SAS® version 9.2 or higher.

---

Document: CP007A SAP.docx

Author: [name]

Version Number:

V 2.0

Version Date:

23 Feb 2017

Template No: CS\_TP\_BS016 – Revision 3

Reference: CS\_WI\_BS005

Effective Date: 01May2012

Copyright © 2012 Quintiles Transnational Corp. All rights reserved.

The contents of this document are confidential and proprietary to Quintiles Transnational Corp. Unauthorized use, disclosure or reproduction is strictly prohibited.

## 7. STATISTICAL CONSIDERATIONS

### 7.1. ADJUSTMENTS FOR COVARIATES AND FACTORS TO BE INCLUDED IN ANALYSES

The following covariates and factors are used in the analyses. For details of their inclusion in the models, see the specific analysis section.

- Pooled site [Pooled Site 01,...,Pooled Site xx]
- Age group [Adolescents/Adults], assigned based on subject's age as entered on the Enrolment Visit CRF for CP007A
- Gender [Male/Female], as collected at the CP007 Screening visit
- Asthma status [Present/Absent], as collected at the CP007 Screening visit
- Baseline score [Represents the Baseline value of the relevant score being analysed], where Baseline is defined as in [Section 6.2](#): Baseline.

### 7.2. MULTICENTRE STUDIES

This study is to be conducted by multiple Investigators at multiple centres internationally.

If a centre has less than five subjects, pooling with other centre(s) is performed based on geographical region, and is to be completed and agreed with Circassia prior to unblinding.

### 7.3. MISSING DATA

Missing safety data will not be imputed.

Missing efficacy data is to be handled as described in [Section 13.1.3](#): Sensitivity Analysis of Primary Efficacy Variable.

---

Document: CP007A SAP.docx

Author: [name]

Version Number:

V 2.0

Version Date:

23 Feb 2017

Template No: CS\_TP\_BS016 – Revision 3

Reference: CS\_WI\_BS005

Effective Date: 01May2012

Copyright © 2012 Quintiles Transnational Corp. All rights reserved.

The contents of this document are confidential and proprietary to Quintiles Transnational Corp. Unauthorized use, disclosure or reproduction is strictly prohibited.

## 7.4. MULTIPLE COMPARISONS/MULTIPLICITY

For the primary hypothesis testing vs. Placebo a Bonferroni-Holm procedure is to be used to adjust alpha in order to compensate for multiplicity when comparing the two Cat-PAD treatment arms vs. Placebo, thereby keeping the overall type I error rate at 0.05. More detail on the procedure is described in [Section 13.1.2: Primary Analysis of Primary Efficacy Variable](#).

Multiple analyses are to be performed as specified in [Section 4: Planned Analyses](#). At each of the statistical analyses performed after one, two, three and four years, there is no adjustment to the significance level, apart from the Bonferroni-Holm correction (due to multiple treatment comparisons) stated above, because analysis of the later years will only be performed if there is a positive outcome in the previous years, and this is, therefore, a hierarchical analysis.

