5.0 STUDY MEDICATION

5.1 Investigational Product

No investigational product will be used in this follow-on study.

Subjects will have received one of the following three study drug regimens in study CP007:

- Single course of Cat-PAD (4 doses of Cat-PAD 6 nmol, 4 weeks apart, followed by 4 doses of placebo, 4 weeks apart)
- Two courses of Cat-PAD (8 doses of Cat-PAD 6 nmol, 4 weeks apart)
- Placebo (8 doses, 4 weeks apart)

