7.4 Statistical Analysis

Further detail of the statistical analyses and data presentations to be used in reporting the study, including dictionaries used for coding and software used, will be provided in the Statistical Analysis Plan (SAP), which will be approved by Circassia prior to performing any analysis of the data.

The nature of the formal statistical testing will be described and justified in the SAP, discussing any potential biases and challenges caused by the data collected and circumstances of the study. It is anticipated that the analyses will be similar to those performed for the CP007 study. For the primary hypothesis testing versus placebo a Bonferroni-Holm procedure will be used to adjust alpha in order to compensate for multiplicity when comparing the two Cat-PAD treatment arms versus placebo, thereby keeping the overall type I error rate at 0.05. The Bonferroni-Holm procedure will assess each of the two treatment comparisons (two courses of Cat-PAD versus placebo and one course of Cat-PAD versus placebo), whereby the smallest p-value (of the two treatment comparisons) will be tested at the 0.05/2 (i.e. $p < 0.025$) alpha level. If this first comparison is statistically significant then the remaining treatment comparison p-value will be tested at the 0.05 alpha level. The tests will be two sided.

If any parametric analyses are found to be inappropriate and/or fail their assumptions then supportive analysis will include non-parametric methods, as appropriate.

All data will be summarised to include the mean, N, SD, median, minimum and maximum values for continuous variables and frequencies and percentages for categorical variables.

The first analysis of the data will be performed on the first year's data after all subjects have completed one year in this study. Additional analyses of the second, third and fourth year in the study will be performed after all subjects have completed each additional year in the study. At each of the statistical analyses performed after one, two, three and four years, there will be no adjustment to the significance level, apart from the Bonferroni-Holm correction (due to multiple treatment comparisons) stated above, because analysis of the later years will only be performed if there was a positive outcome in the previous years, and this is, therefore, a hierarchical analysis.

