## 2. STUDY OBJECTIVES

### 2.1. PRIMARY OBJECTIVE

The primary objective is to evaluate the continued efficacy of Cat-PAD, the first in a new class of Synthetic Peptide Immuno-Regulatory Epitopes, for a total of up to 5 years after the initial administration of treatment in Protocol CP007, based on the reduction of symptoms and the use of allergy medication in subjects previously participating in Protocol CP007.

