## 4. PLANNED ANALYSES

There are four planned unblinded interim analyses.

The first analysis of the data is to be performed on the first year's data after all subjects have either

- Completed their year 1 annual assessment in CP007A
- Discontinued prior to their year 1 annual assessment
- Progressed beyond their year 1 annual assessment regardless of the completion of the assessment

Additional analyses of the second, third and fourth year in the study are to be performed for each relevant year based on the same criteria as above. Analysis of the later years will only be performed if there was a positive outcome in the previous years.

The Quintiles study team, including those responsible for creating the programs to produce the outputs for each analysis, will remain blinded. Once the programs have been produced by the blinded Quintiles study team, these programs are to be sent to an independent statistician at a different geographical location than the blinded team, who will apply the randomisation schedule and provide Circassia with a set of unblinded outputs each year.

Details on independent unblinded team members within Quintiles to perform the analysis and members within Circassia authorised to receive unblinded outputs are specified in a separate Unblinding Plan document.

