### 13.1.2. PRIMARY ANALYSIS OF PRIMARY EFFICACY VARIABLE(S)

The primary objective of this study is to test the hypothesis that there is a difference between either or both Cat-PAD treatment arms and the Placebo arm.

The primary efficacy analysis is to be performed for the FAS.

The least squares (LS) mean difference in mean CS between treatment arms, along with 95% two-sided CIs and p-value are to be estimated by fitting an analysis of covariance (ANCOVA) model, adjusting for the stratification factors listed in [Section 7.1: Adjustments for Covariates and Factors to be Included in Analyses](#).

Additionally, the LS mean and 95% CI for the CS at the CP007 study endpoint of PAC3 is to be calculated for the CP007A FAS subjects using the same ANCOVA. The LS mean and 95% CI is to be presented by treatment arm.

The Bonferroni-Holm procedure is to be utilised to assess each of the two treatment comparisons (two courses of Cat-PAD vs. Placebo and one course of Cat-PAD vs. Placebo), whereby the smallest p-value (of the two treatment comparisons) is to be tested at the 0.05/2 (i.e.  $p < 0.025$ ) alpha level. If this first comparison is statistically significant then the remaining treatment comparison p-value is to be tested at the 0.05 alpha level. The study is to be declared a success if one or more

---

Document: CP007A SAP.docx

Author: [name]

Version Number:

V 2.0

Version Date:

23 Feb 2017

Template No: CS\_TP\_BS016 – Revision 3

Reference: CS\_WI\_BS005

Effective Date: 01May2012

Copyright © 2012 Quintiles Transnational Corp. All rights reserved.

The contents of this document are confidential and proprietary to Quintiles Transnational Corp. Unauthorized use, disclosure or reproduction is strictly prohibited.

treatment arms are statistically significantly different from Placebo.

The differences in LS means for each treatment comparison of active vs. Placebo together with the corresponding two-sided 95% CI and the p-values are to be presented. Additionally p-values are to be calculated and presented for all model effects.

The ratio of LS means along with its 95% CI (calculated by using Fieller's method) is to be presented for evaluation of the clinical significance of active treatment vs. Placebo comparisons.

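### The undefined 'positive outcome' gate protects the study-level test over four annual analyses, but not claims about a named regimen, and the protocol synopsis has no gate at all

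*SAP*

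**What the plan says.** SAP 4 plans four unblinded annual analyses, with this condition: "Analysis of the later years will only be performed if there was a positive outcome in the previous years". SAP 7.4 makes no adjustment beyond Holm because the later analyses "will only be performed if there is a positive outcome in the previous years, and this is, therefore, a hierarchical analysis". Protocol 7.4 gives the same reason: "because analysis of the later years will only be performed if there was a positive outcome in the previous years". The protocol synopsis (Statistical Analysis) also says there is no adjustment beyond Holm, but states no gate.

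SAP 13.1.2 sets the aim as "to test the hypothesis that there is a difference between either or both Cat-PAD treatment arms and the Placebo arm". At each analysis the smaller p-value is tested at 0.025, and then: "If this first comparison is statistically significant then the remaining treatment comparison p-value is to be tested at the 0.05 alpha level". The only success rule in either document follows: "The study is to be declared a success if one or more" arms differ significantly from placebo. No text links that rule to the gate. No text says which arm, endpoint, population or direction makes a year positive, or makes a regimen's later test depend on that regimen's own earlier result.

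**The concern.** A hierarchy spares alpha only for a hypothesis that is tested after its own predecessors have been rejected. If either arm can open the gate, a regimen that failed in Year 1 is tested again in Year 2 because the other one succeeded, and the other's success also releases the full 0.05 to it each time. The claim most useful to a reader of a durability study is that one course, or two courses, still works in year k. The gate was not built to protect that claim. With unblinded outputs going to authorised sponsor staff every year, the meaning of the gate should be settled before the first of them.

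**Working it through.** **Inputs.** From protocol 7.2: difference 0.525 (25% of 2.10), SD 1.29, two-sided alpha 0.025, 266 per arm, and 130 per arm after withdrawals. From SAP 13.1.2 and SAP 4: Holm at 0.025 then 0.05, four analyses. Not in the documents and therefore assumed: between-year correlation of a subject's score 0.5–0.9 (0 as an extreme), and an attrition path of 266/221/175/130. Ranges below cover 266 per arm, 130 per arm and that path. Error rates are simulated: three arms sharing placebo, nested attrition, z tests.

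**1. The plan's own figures.** Holm: 0.025 + 0.025 = 0.05. Power: noncentrality = 0.525 / (1.29 × √(2/n)), which is 4.69 at n = 266 and 3.28 at n = 130. Power at 0.025 by the noncentral t is 99.3% and 84.7%, consistent with the stated 99% and 80%.

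**2. Study level, either-arm gate.** Take the first year in which neither regimen works. A false study-level claim needs a rejection in that year, and Holm bounds this at 0.05. Simulated: at most about 4.8%. The word 'hierarchical' is correct here.

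**3. Named regimen, either-arm gate, all regimen-by-year claims counted.** If the working regimen always opens the gate, the inert one is tested at 0.05 four times. With independent years the limit is 1 − 0.95⁴ = 18.5%. Correlation lowers it:

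| Scenario (effect 0.525) | Two-sided | In favour of Cat-PAD |
|---|---|---|
| One works all four years, other inert | 7.5–15.2% | 4.6–8.1% |
| One lasts, other works in Year 1 only | 6.0–12.4% | 4.1–6.4% |
| One works in Year 1 only, other inert | 5.8–8.9% | 3.8–4.5% |
| Both work in Year 1 only | 3.4–4.7% | 2.2–2.5% |

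Nominal values are 5% and 2.5%. In the first scenario the inert regimen fails Year 1 and is tested again in Year 2 in 94% of trials at 266 per arm and 81% at 130.

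**4. Only unbroken claims counted** (the regimen was significant in every year so far).
- One works throughout, other inert: at most 5.0% two-sided, about 2.5% favourable.
- One lasts, other wanes: about 5% or less.
- Both wane: no excess, as in the table.
- Working regimen loses its effect after Year 1 or 2, other inert: 5.4–7.6% two-sided (the top of the range is at correlation 0), 3.5–3.8% favourable. Roughly, the inert regimen is tested at 0.05 in Year 1, then the waned one at about 0.025 in its first null year: 0.05 + 0.95 × 0.025 = 7.4%.

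**5. The synopsis read literally (no gate).** With neither regimen ever working, the chance of at least one false rejection over four years is 9.0% at correlation 0.9, 14.9% at 0.5 and 17.4% at 0. On that text even the study-level error fails.

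**6. Candidate repairs.**
- Regimen-specific gate with Holm reset to 0.05 each year: the inert regimen drops out after Year 1, and the waned one is then tested alone at 0.05. The limit is 1 − 0.95² = 9.75%; simulated 6.5–9.7%. Not enough.
- Separate Year 1–4 sequences at 0.025 each, with 0.025 passed on only after a full sequence is rejected: 5.0% or less in every scenario run.

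**The case against.** The strongest reply is that the benchmark is imported. SAP 13.1.2 states its hypothesis for either or both arms and declares success on one or more. The primary objective ("The primary objective is to evaluate the continued efficacy of Cat-PAD") names no regimen, and neither document promises error control over a regimen-by-year family. On that hypothesis the plan is sound. A regimen that failed in Year 1 and is significant only later is also not showing continued efficacy, so the upper rates count claims outside the objective. The lead scenario pairs a fully effective regimen with an inert one, although the two share their first four active doses (protocol 5.1). Finally, SAP 7.4 sends the reader to 13.1.2 for the Holm procedure, so its success rule is the natural meaning of a positive outcome.

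Much of this stands. It rules out a conclusion a reader might draw from the table, that the trial's overall type I error is 15%. The documents do not support that: the hypothesis they state is controlled, and within any single year Holm controls the regimen claims too.

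Three things survive. Each regimen gets its own yearly test, p-value and interval, and no text limits what may be claimed from them. The gate is still formally undefined; because the tests are two-sided and the success rule says only that arms differ, a significantly worse arm would literally open it. And the synopsis contradicts protocol 7.4.

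**Conclusion.** The concern holds in a limited form. *Positive outcome* is undefined, it is the sole reason for no adjustment across years, and the synopsis omits it. On the either-arm reading, the study-level hypothesis is controlled (at most about 4.8%), but a claim that a named regimen works in a given year is not.

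The size depends on what is claimed. Counting every regimen-by-year claim, error is about 7.5–15% two-sided with one lasting and one inert regimen. Counting only unbroken efficacy, it is nominal if the working regimen lasts or both wane, and 5.4–7.6% if the working regimen's effect is lost after Year 1 or 2 and the other is inert. These figures rest on the assumed correlation and attrition and on the either-arm reading. A both-arms gate would control the error, but no text states one. This should be fixed; it does not invalidate the study-level test.

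**What to change.** Before the first unblinded analysis, amend SAP 4, 7.4 and 13.1.2, protocol 7.4 and the synopsis.

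(a) Define a positive outcome as a statistically significant difference in favour of Cat-PAD on the mean Combined Score in the FAS. Add the gate to the synopsis so that it agrees with protocol 7.4.

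(b) Then choose one of two routes:
- **Study-level claims only.** Limit the confirmatory conclusion across years to 'at least one regimen works in year k', and label regimen-by-year p-values after Year 1 as nominal. This needs only wording. The Year 1 regimen claims and the study-level sequence are then two separate 5% statements, not one joint one.
- **Regimen-level claims.** Test each regimen in its own Year 1–4 sequence at two-sided 0.025, in year k only if that regimen was itself significant in every earlier year. Pass the 0.025 to the other regimen only after a full four-year sequence is rejected; its stored p-values are then read in order at 0.05. Do not reset Holm each year.

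The second route has two costs. Single-year power at 130 per arm is 84.7% at 0.025 against 90.5% at 0.05, still above the stated 80%, and protocol 7.2 already plans at 0.025. The second regimen also cannot use 0.05 until after Year 4. Neither route needs new data.
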